9.3 POPULATIONS FOR ANALYSES

- ICF Dataset: All families who were approached for study participation
- Intention-to-Treat (ITT) Dataset: all consented infants
- Modified Intention-to-Treat Dataset: all consented infants for whom both NewbornDx and rWGS genomic sequencing results were returned
- Per-Protocol Dataset: all consented infants who received both NewbornDx and rWGS (modified intention-to-treat dataset) and completed the study period for the analysis of the primary and secondary objectives without clinically important protocol deviations. Clinically important protocol deviations will be identified and documented prior to the database lock.
- Time to Molecular Diagnosis Dataset: The Modified Intention-to-Treat Analysis Dataset excluding the infants who did not have a confirmed positive result
- Urgent Testing Dataset: All infants who required urgent testing per section 8.1

- Safety Analysis Dataset: All infants for whom blood specimens were obtained or data collected

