9.4 STATISTICAL ANALYSES

9.4.1 GENERAL APPROACH

All analyses will be descriptive. We will calculate the proportion and 95% CI among enrolled infants with confirmed genetic disorders detected by NewbornDx, by rWGS, by NewbornDx but not rWGS, and by rWGS but not NewbornDx. We will also calculate the 95% CI for the ratio of the proportion detected by NewbornDx relative to the proportion detected by rWGS⁶⁹. Although detection by SOC is an exclusion criterion, some infants will receive a diagnosis by SOC after enrollment. We will therefore also calculate the proportion and 95% CI of those receiving a diagnosis by SOC prior to the time that results from NewbornDx or rWGS become available. We will calculate the proportions and CIs for enrollees with no confirmed diagnosis of a genetic disorder. These will be calculated at discharge and at 1 year CGA. We will calculate the proportion of infants with conditions detected by NewbornDx that were not listed as part of the differential diagnosis at enrollment. The same calculation will be performed for rWGS. We will calculate the positive predictive value (PPV) of NewbornDx and rWGS (i.e. the proportion of positives that are confirmed by Sanger or PCR).

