Because a “gold standard” does not currently exist, it will not be possible to calculate the negative predictive value (NPV), sensitivity, or specificity of NewbornDx or rWGS. We will calculate the proportion for which there was clinical utility from genomic testing (change in drug treatment, surgical treatment, imaging, subspecialty consult, diet, other treatment, and redirection of care and/or withdrawal of life sustaining treatment). We will also calculate the proportion of testing where trios were ultimately required to confirm a diagnosis for rWGS and if this approach increased the number with a confirmed diagnosis. Kaplan-Meier (K-M) curves will be used to estimate the time from enrollment to molecular diagnosis (separately for NewbornDx and rWGS) including all enrolled infants and excluding infants without a diagnosis of a genetic disorder and those diagnosed by SOC before genomic results are returned. The analysis will count as positive only those diagnoses that are eventually confirmed. We will also use K-M to estimate age at diagnosis and survival. A model will be developed to predict, using information available at the start of symptoms, whether the NewbornDx ultimately yields a confirmed and actionable diagnosis. Such a model could help to further target NewbornDx to the population that would benefit most from it, especially if the model discrimination is high (c-statistic greater than .90). The model will be validated using bootstrap validation.

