9.4.2 ANALYSIS OF THE PRIMARY EFFICACY ENDPOINT(S)

Primary Endpoints	Definition	Scale and measure	Populations for which the analysis will be conducted
A confirmed positive result detected by NewbornDx	If NewbornDx and the confirmatory test have the same positive finding	Binary: Yes/No; single endpoint	Modified Intention-to-Treat Dataset
A confirmed positive result detected by rWGS	If rWGS and the confirmatory test have the same positive finding	Binary: Yes/No; single endpoint	Modified Intention-to-Treat Dataset
Time to a positive result by NewbornDx *	Among those who have a confirmed positive result at one year CGA by NewbornDx, rWGS, or another genetic test, comparison of date/time of sample collection to date/time of completion of NewbornDx prior to confirmation testing	Interval: Hours; single endpoint	Time to Molecular Diagnosis Dataset
Time to a positive result by rWGS*	Among those who have a confirmed positive result at one year CGA by NewbornDx, rWGS, or another genetic test, comparison of date/time of sample collection to date/time of completion of rWGS prior to confirmation testing	Interval: Hours; single endpoint	Time to Molecular Diagnosis Dataset
Time to a result by NewbornDx*	Among all babies tested, comparison of date/time of sample collection to date/time of completion of NewbornDx prior to confirmation testing	Interval: Hours; single endpoint	Modified Intention-to-Treat Dataset
Time to a result by rWGS*	Among all babies tested, comparison of date/time of sample collection to date/time of completion of rWGS prior to confirmation testing	Interval: Hours; single endpoint	Modified Intention-to-Treat Dataset
Time from enrollment to a positive result	Among those who have a confirmed positive results at one year CGA by NewbornDx, rWGS or another genetic test,	Interval: Hours; single endpoint	Time to Molecular

Primary Endpoints	Definition	Scale and measure	Populations for which the analysis will be conducted
detected by NewbornDx*	comparison of date/time of informed consent to date/time of completion of NewbornDx prior to confirmation testing		Diagnosis Dataset
Time from enrollment to a positive result detected by rWGS*	Among those who have a confirmed positive results at one year CGA by NewbornDx, rWGS, or another genetic test, comparison of date/time of informed consent to date/time of completion of rWGS prior to confirmation testing	Interval: Hours; single endpoint	Time to Molecular Diagnosis Dataset

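### The Kaplan-Meier sentence in 9.4.1 leaves the risk set unclear, does not match 9.3 and 9.4.2, and any curve without undiagnosed and SOC-first infants shows turnaround among positives, not time to diagnosis

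*Combined protocol and SAP*

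**What the plan says.** Section 9.4.1 (General approach) states: "Kaplan-Meier (K-M) curves will be used to estimate the time from enrollment to molecular diagnosis (separately for NewbornDx and rWGS"), and gives the population as "including all enrolled infants and excluding infants without a diagnosis of a genetic disorder and those diagnosed by SOC before genomic results are returned". On the event it adds: "The analysis will count as positive only those diagnoses that are eventually confirmed". It states no censoring or competing-event rule for final negative results, SOC diagnoses or deaths.

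Other places define related sets differently:

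- **9.3, Time to Molecular Diagnosis Dataset:** "The Modified Intention-to-Treat Analysis Dataset excluding the infants who did not have a confirmed positive result". There is no SOC-first exclusion.
- **9.4.2, time to a positive result:** "Among those who have a confirmed positive result at one year CGA by NewbornDx, rWGS, or another genetic test". An infant diagnosed by an SOC genetic test can therefore be included.
- **9.4.2, time to a result:** "Among all babies tested, comparison of date/time of sample collection to date/time of completion of NewbornDx prior to confirmation testing", with a matching row for rWGS. This is turnaround of any result.
- **9.4.1, earlier in the same section:** "Although detection by SOC is an exclusion criterion, some infants will receive a diagnosis by SOC after enrollment". The share of these infants is to be reported with a CI. So is the undiagnosed share: "We will calculate the proportions and CIs for enrollees with no confirmed diagnosis of a genetic disorder".
- **7.1 and 7.2:** under 7.1 an infant whose clinical diagnosis comes before testing is complete will be withdrawn; 7.2 lists the same situation as one in which the investigator may withdraw the infant. Under 7.2, testing continues after an infant's death unless the parent or guardian objects.

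**The concern.** Timeliness is a primary endpoint, and 9.1 rules out hypothesis tests, so the estimated times are themselves the result. Two analysts working from the 9.4.1 sentence could draw different curves.

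Both exclusions use information that arises after enrollment. Whether an infant is ever diagnosed is a later outcome. Whether SOC came first depends on how slow the genomic result was, so that exclusion removes long times preferentially. A curve built this way answers how long a positive result took among infants who had one and were not overtaken. It does not answer how soon an enrolled infant can expect a diagnosis.

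If an all-enrolled curve is also meant, its shape depends on what happens to infants who can no longer have the event. Censoring them gives them the same future chance of diagnosis as infants still waiting for a result.

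**Working it through.** **Inputs.** From the documents: 400 infants with 40% to 60% diagnosed (9.2); NewbornDx results returned in 13 days on average in the preliminary study (2.2); an SOC diagnosis in 15% in the neonatal period (2.1). Assumed: the shape of the turnaround distribution, the same distribution for positives and negatives, and SOC time independent of genomic time. No turnaround figure for rWGS is used.

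**The plan's own figure.** 400 × 0.40 = 160 and 400 × 0.60 = 240, as 9.2 states. The plan gives no Kaplan-Meier median or curve to reproduce.

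**Step 1: dropping undiagnosed infants.** Let F(t) be the turnaround distribution and p the diagnosed share. With everyone kept at risk the curve is p·F(t); restricted to diagnosed infants it is F(t). The ratio is 1/p, from 1/0.60 = 1.67 to 1/0.40 = 2.5. With mean 13 days:

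| Shape of F | Restricted median | All-enrolled median, p = 0.60 (F = 0.5/0.6) | F(14) |
|---|---|---|---|
| Lognormal, CV 0.5 | 11.6 d | 18.4 d | 0.65 |
| Gamma, shape 4 | 11.9 d | 19.0 d | 0.62 |
| Exponential | 9.0 d | 23.3 d | 0.66 |

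By day 14 the restricted curve shows 62% to 66% diagnosed. The all-enrolled curve shows between 0.40 × 0.62 = 25% and 0.60 × 0.66 = 40%. For p below 0.50 its median is never reached.

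**Step 2: dropping SOC-first infants.** Take SOC time as exponential with 15% diagnosed by 28 days, a rate of −ln(0.85)/28 = 0.0058 per day. Exclude infants whose SOC time is shorter than their lognormal genomic time. By simulation:

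| Calibration | log-SD | Median before → after | Change |
|---|---|---|---|
| Median 13 d | 0.5 | 13.0 → 12.7 d | about 0.3 d |
| Median 13 d | 0.8 | 13.0 → 12.3 d | about 0.7 d |
| Mean 13 d | 0.5 | 11.5 → 11.3 d | about 0.2 d |
| Mean 13 d | 0.8 | 9.4 → 9.1 d | about 0.4 d |

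The mean-13 rows fit the documents better, because 2.2 reports an average. If the SOC-first share is instead fixed at 5% to 15% of diagnosed infants, with the three shapes of Step 1, the median shortens by 0.1 to 1.4 days; the upper end comes from the exponential shape.

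**Step 3: an all-enrolled curve with negatives censored at their result.** The plan does not state this rule; the step shows why a rule is needed. The hazard of a positive result is p times the hazard of any result, so Kaplan-Meier estimates 1 − (1 − F)^p, while the true share diagnosed is p·F. At F = 0.90:

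- p = 0.40: 1 − 0.10^0.40 = 60%, against 36%
- p = 0.50: 1 − 0.10^0.50 = 68%, against 45%
- p = 0.60: 1 − 0.10^0.60 = 75%, against 54%

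**The case against.** The strongest reply is that the sentence may well mean two analyses, one on all enrolled infants and one restricted, in which case the exclusions touch only the second. Time among positives is a legitimate description: the protocol names time from sample collection to a positive result as an endpoint, and 9.2 sizes the diagnosed group. Sections 9.3 and 9.4.2 already plan that description without a SOC-first exclusion, and 9.4.1 reports the undiagnosed and SOC-first shares with CIs. The listed primary timeliness analyses are those in 9.4.2; the 9.4.1 curves are additional.

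Most of this stands. A reader might infer that the plan contradicts itself outright, but the two-analysis reading is natural, so the text supports only ambiguity and a mismatch with 9.3 and 9.4.2. A reader might also infer that every planned time estimate is biased toward speed; that applies to the restricted curve only, and only if it is presented as time to diagnosis for enrolled infants.

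What the reply leaves open is the missing rule for negatives, SOC-first withdrawals and deaths in an all-enrolled curve, and the SOC-first exclusion itself. Reporting the excluded shares beside the curve helps the reader but does not change the curve.

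**Conclusion.** The point holds in limited form. The 9.4.1 sentence does not fix the risk set and does not match 9.3 and 9.4.2. A curve without undiagnosed and SOC-first infants conditions on post-enrollment outcomes and should be read as turnaround among positives. Relative to an all-enrolled curve, dropping undiagnosed infants raises it 1.67- to 2.5-fold over the 9.2 yield range, assuming equal turnaround for positives and negatives. The SOC-first exclusion adds a small shortening, roughly 0.2 to 0.7 days in the median; this rests on assumed lognormal shapes, a NewbornDx-only average, and a neonatal-period SOC rate applied to the 28 days after enrollment.

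The 68% against 45% should not be read as what the trial will report. It would follow only if negatives were censored at their result, and no section says so. It shows what depends on the unstated rule.

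Death is not automatically a competing event here, because 7.2 continues testing after death unless the parent or guardian objects.

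**What to change.** 1. State in 9.4.1 whether one or two analyses are meant.
2. For the all-enrolled analysis, use cumulative incidence (Aalen-Johansen) of confirmed diagnosis from consent, separately per platform. Keep infants with a negative result in the risk set to 1 year CGA. Treat as competing events only those that stop testing: withdrawal after an SOC diagnosis, or death where the parent or guardian declines further testing.
3. Remove the SOC-first exclusion from the restricted analysis, label it as turnaround among confirmed positives, and align it with 9.3 and 9.4.2, so that SOC-first infants whose genomic test was completed are included.
4. Reconcile 7.1 and 7.2 on withdrawal when a clinical diagnosis precedes test completion, both with each other and with the analyses in 9.4.1 and 9.4.2 that rely on these infants.

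**Cost:** wording, standard software and a little more analysis work. Sample size is unaffected, because the plan is descriptive. One limit remains: SOC-first infants withdrawn before test completion contribute no genomic completion time, so they can enter the all-enrolled analysis as competing events but not the turnaround analysis.

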9.4.2 ANALYSIS OF THE PRIMARY EFFICACY ENDPOINT(S)

Primary Endpoints	Definition	Scale and measure	Populations for which the analysis will be conducted
A confirmed positive result detected by NewbornDx	If NewbornDx and the confirmatory test have the same positive finding	Binary: Yes/No; single endpoint	Modified Intention-to-Treat Dataset
A confirmed positive result detected by rWGS	If rWGS and the confirmatory test have the same positive finding	Binary: Yes/No; single endpoint	Modified Intention-to-Treat Dataset
Time to a positive result by NewbornDx *	Among those who have a confirmed positive result at one year CGA by NewbornDx, rWGS, or another genetic test, comparison of date/time of sample collection to date/time of completion of NewbornDx prior to confirmation testing	Interval: Hours; single endpoint	Time to Molecular Diagnosis Dataset
Time to a positive result by rWGS*	Among those who have a confirmed positive result at one year CGA by NewbornDx, rWGS, or another genetic test, comparison of date/time of sample collection to date/time of completion of rWGS prior to confirmation testing	Interval: Hours; single endpoint	Time to Molecular Diagnosis Dataset
Time to a result by NewbornDx*	Among all babies tested, comparison of date/time of sample collection to date/time of completion of NewbornDx prior to confirmation testing	Interval: Hours; single endpoint	Modified Intention-to-Treat Dataset
Time to a result by rWGS*	Among all babies tested, comparison of date/time of sample collection to date/time of completion of rWGS prior to confirmation testing	Interval: Hours; single endpoint	Modified Intention-to-Treat Dataset
Time from enrollment to a positive result	Among those who have a confirmed positive results at one year CGA by NewbornDx, rWGS or another genetic test,	Interval: Hours; single endpoint	Time to Molecular

Primary Endpoints	Definition	Scale and measure	Populations for which the analysis will be conducted
detected by NewbornDx*	comparison of date/time of informed consent to date/time of completion of NewbornDx prior to confirmation testing		Diagnosis Dataset
Time from enrollment to a positive result detected by rWGS*	Among those who have a confirmed positive results at one year CGA by NewbornDx, rWGS, or another genetic test, comparison of date/time of informed consent to date/time of completion of rWGS prior to confirmation testing	Interval: Hours; single endpoint	Time to Molecular Diagnosis Dataset
Clinical utility of genomic sequencing	If clinical action was taken due to return of results Time from result to action taken Types of clinical actions taken (i.e. surgery, medication) Clinician opinion of utility	Binary: Yes/No Interval Categorical Ordinal	Modified Intention-to-Treat Analysis Dataset
If trio testing was required to obtain a diagnosis for rWGS	If Trios were done If Trios increased diagnostic yield	Binary: Yes/No; single endpoint Binary: Yes/No; single endpoint	Modified Intention-to-Treat Analysis Dataset
If enrollees did not receive a diagnosis	No confirmed diagnosis of a genetic disorder identified by any of the genomic sequencing tests	Binary: Yes/No; single endpoint	Modified Intention-to-Treat Analysis Dataset

*The infants who met the criteria for urgent testing may be analyzed separately.

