- To develop and qualitatively assess the web-based clinical reference database of supporting information for medical providers and parents

Endpoints:

Primary Endpoints:

- A confirmed genetic disorder detected by NewbornDx
- A confirmed genetic disorder detected by rWGS
- Time from sample collection to positive test result
- Clinical utility of genomic sequencing (care changes, time to initiation of appropriate treatment or redirection of care including the withholding or withdrawing of life-sustaining treatment)

Secondary Endpoints:

- One-year cost-effectiveness of SOC, NewbornDx and rWGS testing
- Lifetime cost-effectiveness of SOC, NewbornDx and rWGS testing
- User satisfaction with the clinical reference database

Study Population:

400 infants less than one year corrected gestational age (CGA) admitted to a hospital (NICU/PICU/ CICU/inpatient floor) participating in this study with signs/symptoms consistent with a possible genetic disorder

Phase:

N/A

Enrolling Sites:

The Floating Hospital for Children at Tufts Medical Center, Cincinnati Children's Hospital Medical Center, Mount Sinai - Kravis Children's Hospital, Children's Hospital of Pittsburgh, Rady Children's Hospital - San Diego, and North Carolina Children's Hospital

[figure not shown]
Study Duration:

54 months

[figure not shown]
Participant Duration:

From enrollment until 1 year CGA

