Misinterpretation of results: We expect to miss a small number of structural variants (SVs) using short read rWGS (NewbornDx does not detect structural variants) that are causal. We will monitor the percentage of identified SVs and be careful not to label cases with a negative result as not genetic in origin. Experienced personnel will perform the genomic testing according to well-established protocols. Although we may not find a result, this does not mean the infant will not continue to have symptoms or even have a genetic disorder. Similarly, the infant’s health may not improve during this study; it may get worse or stay the same. All infants will continue to receive routine care as directed by the clinical team, including routine NBS and other genetic testing.

Risk of discrimination associated with genetic testing: Federal and State laws generally make it illegal for health insurance companies, group health plans, and most employers to discriminate against a person based on their genetic information. The Genetic Information Non-discrimination Act (GINA) indicates that genetic information cannot be used by certain health insurance companies when making decisions about eligibility for health insurance or how much insurance costs. These insurance companies can still use any genetic information to help them decide whether or not they will pay health insurance claims. This law also indicates that employers with fifteen or more employees may not use genetic information when making decisions to hire, promote, or fire an individual or when setting the terms of employment. Protections by this law may not apply to certain military, veterans and federal employees. These laws do not protect against genetic discrimination by companies that sell life, disability, or long-term care

insurance. Information regarding the protections and limitations of Genetic Information Nondiscrimination Act (GINA) will be included in the ICF.

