3 OBJECTIVES AND ENDPOINTS

Primary Objectives	Endpoints		Endpoint Justification
To estimate the diagnostic yield of NewbornDx and rWGS in identifying genetic disorders of unknown etiology	Primary	A confirmed genetic disorder detected by NewbornDx A confirmed genetic disorder detected by rWGS	Assess diagnostic capability of the platforms
	Secondary	For diagnoses by rWGS, if trio testing was required to confirm a diagnosis	Assess need for including biological parents
To assess the clinical utility of genomic sequencing	Primary	Time from sample collection to positive test result	Assess the timeliness of an accurate result
	Primary	Clinical utility of genomic sequencing	Assess impact on care
	Secondary	If the infant does not receive a diagnosis, calculated at discharge and at 1year CGA	Assess the clinical impact of platform(s)
Secondary Objectives	Endpoints		Endpoint Justification
To examine the economic impact and health outcomes of NewbornDx and rWGS in infants compared with SOC diagnostic testing, over a one-year and lifetime horizon	Secondary	One-year cost-effectiveness of NewbornDx and rWGS compared with SOC testing	Assess economic value of alternative testing strategies
	Secondary	Lifetime cost-effectiveness of NewbornDx and rWGS, compared with SOC testing	Assess economic value of alternative testing strategies
To develop and qualitatively assess the web-based clinical reference database of supporting information for medical providers and parents	Secondary	Satisfaction of the web-based clinical reference database	Assess ease of use and usefulness of information among medical providers
Exploratory Objectives	Endpoints		Endpoint Justification
To inform the NewbornDx panel with findings from rWGS that were not identified with NewbornDx	Exploratory	Conditions detected by rWGS that were not detected by NewbornDx	Expand and improve the diagnostic accuracy of the NewbornDx panel

How endpoint(s) will be adjudicated

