9.2 SAMPLE SIZE DETERMINATION

The sample proportion and 95% CI for the binary outcomes of NewbornDx and rWGS will be calculated. The table below shows the 95% confidence limits of the estimated proportion for a range of proportions, assuming the sample size is 400 completed infants. For example, if the sample proportion is 0.05 for disorders detected by rWGS but not NewbornDx, the 95% CI will be 0.03 to 0.07. Since the distribution of time to diagnosis is unknown, it is difficult to speculate as to the width of the confidence interval for the mean or median. However, 40% to 60% (160 to 240 infants) are expected to have a genetic diagnosis which is a sufficient number for a precise estimate.

Table: Confidence Interval Limits with 400 infants

Proportion	Lower Limit	Upper Limit
0.05	0.03	0.07
0.10	0.07	0.13
0.20	0.16	0.24
0.30	0.25	0.35
0.40	0.35	0.45
0.50	0.45	0.55

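### Four primary timing rows are titled as time to a positive result of NewbornDx or rWGS but are defined as completion of that test in infants positive by any test

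*Combined protocol and SAP*

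**What the plan says.** The synopsis lists "Time from sample collection to positive test result" as a primary endpoint. Section 3 places it under clinical utility, with the justification "Assess the timeliness of an accurate result".

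Section 9.4.2 turns this into several rows. Four of them carry titles about a positive result by, or detected by, NewbornDx or rWGS. The two sample-collection rows select infants "Among those who have a confirmed positive result at one year CGA by NewbornDx, rWGS, or another genetic test"; the two enrollment rows use nearly the same words with the same meaning. In all four the clock stops at completion of the named test, before confirmation testing.

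These rows use the Time to Molecular Diagnosis Dataset, which 9.3 describes as "The Modified Intention-to-Treat Analysis Dataset excluding the infants who did not have a confirmed positive result". It does not say by which test.

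Two further rows give time to any result. The NewbornDx one reads "Among all babies tested, comparison of date/time of sample collection to date/time of completion of NewbornDx prior to confirmation testing".

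**The concern.** Title and definition describe different quantities. The title promises the time until the named test gave a positive. The definition gives the time until the named test was finished, in infants whom some test eventually diagnosed. An infant with a negative NewbornDx report and a confirmed rWGS diagnosis meets the definition of the NewbornDx-positive row. Read literally, an infant diagnosed only by another genetic test enters all four rows.

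The plan allows for such infants. Section 2.3.1 states that "NewbornDx does not detect structural variants", and the confirmatory-testing table in 6.1.1 lists structural variants as found by rWGS only (although 2.2 credits the panel with detecting copy number variants). Section 9.4.1 plans to report the proportion found by rWGS but not NewbornDx.

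At stake is what is published under a primary label. Two analysts, one following the title and one the definition, would report different numbers for the same endpoint.

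**Working it through.** **Does any other text repair the definition?**

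- Dataset (9.3): names no test, so it does not restrict the rows.
- The phrase about timing before confirmation: the all-infant rows use it too, so it does not imply a positive.
- Yield rows (9.4.2): these require the named test and its confirmatory test to share the same positive finding. The plan therefore has a test-specific definition of positivity, but the timing rows do not use it.
- All-infant timing rows: they do not isolate positives.
- Kaplan-Meier text (9.4.1): separate curves per test, counting only diagnoses that are eventually confirmed. They may give a test-specific time to diagnosis, but they start at enrollment.

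So no row in 9.4.2 isolates positives of the named test, and nothing else does so from sample collection.

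**The plan's own figures.** Section 9.2 says "40% to 60% (160 to 240 infants) are expected to have a genetic diagnosis": 0.40 × 400 = 160 and 0.60 × 400 = 240, as stated. It also says "if the sample proportion is 0.05 for disorders detected by rWGS but not NewbornDx, the 95% CI will be 0.03 to 0.07": 0.05 ± 1.96 × √(0.05 × 0.95 / 400) gives 0.0286 to 0.0714, which rounds to the stated limits.

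**Share of non-positive times.** Assumption: every diagnosed infant is rWGS-positive. Then the infants found by rWGS only are exactly those who bring a non-positive time into the NewbornDx rows.

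- Plan's illustration: 0.05 × 400 = 20 infants; 20/240 = 8.3% and 20/160 = 12.5%.
- Over the interval of that illustration: 0.03 × 400 = 12, 12/240 = 5.0%; 0.07 × 400 = 28, 28/160 = 17.5%.
- Using the in-silico overlap of 85% to 94% in 2.2 (variant-level, so only a proxy): 6% to 15%.
- At full overlap, with no diagnosis by another test alone: 0%.

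Under this assumption the rWGS rows are unaffected. They change only through infants diagnosed by NewbornDx alone or by another test alone, for which the documents give no figure.

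**Effect on the median.** Let p be the share of non-positive times, m the reported median, and F₊ and F₋ the distribution functions of the positive and non-positive times. Then 0.5 = (1 − p)·F₊(m) + p·F₋(m). Since F₋(m) lies between 0 and 1, F₊(m) lies between (0.5 − p)/(1 − p) and 0.5/(1 − p).

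- p = 0.083: 45.5% to 54.5%.
- p = 0.125: 0.375/0.875 = 42.9% to 0.5/0.875 = 57.1%.
- p = 0.175: 0.325/0.825 = 39.4% to 0.5/0.825 = 60.6%.

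For scale, the distribution-free 95% confidence interval for a median at n = 160 runs from rank 68 to rank 93, that is 68/160 = 42.5% to 93/160 = 58.1%. At the plan's illustration the worst case lies inside this range. At the upper limit of the illustration's interval it is slightly wider.

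**The case against.** The strongest reply is that the common set is deliberate. All four rows list the same three sources of diagnosis, which suits a comparison of the two tests' turnaround in the same diagnosed infants. That is a coherent quantity, and if it was intended the fault lies in the labels. This stands as a choice of remedy, but does not remove the mismatch.

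Second, the synopsis says only that the test result is positive; it does not say of which test. A reader might infer that the synopsis itself promises a test-specific time, but that comes only from the row titles in 9.4.2. What remains is that completion of a non-positive report is not a positive test result under either wording.

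Third, a reader might infer that a test-specific time to diagnosis is planned nowhere. The Kaplan-Meier text in 9.4.1 arguably supplies one from enrollment. It does not state how infants negative on the named test are handled, but that is missing detail rather than an error.

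Fourth, a reader might take the 60% in Hypothesis #1 and conclude that 40% of the NewbornDx times (64 of 160, or 96 of 240) are non-positive and the median badly distorted. The documents do not support this. The 60% is a hypothesised minimum, not an expectation, and a large distortion also needs nearly all non-positive times to fall on one side of the median. No completion times by result status are given, and because the clock stops before confirmation, the extra delay of confirming positives is excluded. The true shift could be nil.

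Finally, the harm is limited: 9.1 rules out hypothesis testing, 9.4.1 reports yield and rWGS-only detections separately, and all-infant turnaround has its own rows. That is correct and bounds the importance of the point.

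**Conclusion.** The four rows are wrong as written: their definitions match neither their titles nor the endpoint in the synopsis and section 3. The consequence is confined to the labelling and content of descriptive timing results. If all diagnosed infants are rWGS-positive, the plan's illustration puts 8.3% to 12.5% non-positive times in the NewbornDx rows. The worst-case reported median then lies between about the 43rd and 57th percentiles of the true positive times, no further out than sampling error at n = 160. The illustration shows interval width and is not a forecast. The bias in hours and its direction cannot be computed from the documents. Yield endpoints and sample size are unaffected. The wording should still be corrected, because these are primary endpoints and the correction is cheap.

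**What to change.** Align title and definition in one of two ways, or report both.

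**(a) Restrict.** Limit each row, and the dataset it uses in 9.3, to infants with a confirmed positive at one year CGA by the named test. Stop the clock at the preliminary determination of the analysis that produced that positive. This must be explicit because 6.1.1 allows an infant-only rWGS analysis to be followed by a duo or trio analysis, and allows reanalysis after a change in phenotype, and 8.2 allows variants of unknown significance to be re-analysed at the end of the study. State that the NewbornDx and rWGS rows then rest on different infants and are not a paired comparison.

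**(b) Retitle.** Keep the common any-test-positive set and call the rows *turnaround time of NewbornDx (rWGS) among diagnosed infants*. If (b) is used alone, reword the endpoint in the synopsis and section 3 to match.

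**Cost.** No new data: the Schedule of Activities already has each laboratory send the preliminary result, the time it was determined, whether it came from infant-only, duo or trio data, and whether it was confirmed. Option (b) loses no infants. Under (a), on the same assumption and illustration, the NewbornDx rows fall to 160 − 20 = 140 or 240 − 20 = 220 infants. At n = 140 the 95% interval for the median runs from rank 58 to rank 83 (41.4% to 59.3%), against 42.5% to 58.1% at n = 160, a small loss of precision.
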